#### 4.7.1 Immunogenicity analyses

Participant's antidrug antibodies (ADA) status, response variable (see definitions below) will be summarized in the ADA population.

Sample status (negative, positive, inconclusive) and titers will also be described overtime using descriptive statistics.

The impact of positive immune response on efficacy, PK and safety variables may be further explored, depending on ADA incidence.

##### **Participant's ADA status**

- Participants with **pre-existing ADA** correspond to participants with ADAs present in samples drawn before first IMP administration. Participants with missing ADA sample at baseline will be considered as without pre-existing ADA.
- Participants with **treatment-emergent ADA** correspond to participants with at least one treatment-induced/boosted ADA.
  - Participants with **treatment-induced ADA** correspond to participants with ADAs that developed during the treatment-emergent period and without pre-existing ADA (including participants without pre-treatment samples).
  - Participants with **treatment-boosted ADA** correspond to participants with pre-existing ADAs that are boosted during the treatment-emergent period to a significant higher titer than the baseline. A 3-fold serial dilution schema is used during titration, so at least a 9-fold increase of titer values will be considered as significant.
- Participants **without treatment-emergent ADA** correspond to participants without treatment-induced/boosted ADA during the treatment-emergent period.
- Participants **with inconclusive ADA** are defined as participants which cannot irrefutably be classified as with or without treatment-emergent ADA.

##### **ADA response variable:**

- **ADA incidence** is defined as the proportion of participants found to have seroconverted (treatment-induced ADAs) or boosted their pre-existing ADA response (treatment-boosted ADAs) at any time point during the treatment-emergent period.

#### 4.8 INTERIM ANALYSES

An interim analysis (IA) will be conducted when approximately 12 participants have each been treated for 15 weeks.

## 5 SUPPORTING DOCUMENTATION

### 5.1 APPENDIX 1 LIST OF ABBREVIATIONS

ADA:	antidrug antibodies
AE:	adverse event
ALT:	alanine aminotrasferase
ANA:	antinuclear antibody
aPTT:	activated partial thromboplastin time
AST:	aspartate aminotrasferase
ATC:	anatomic category, anatomic or therapeutic category
BMI:	body mass index
BUN:	blood urea nitrogen
CI:	Confidence Interval
CIC:	circulating immune complexes
Covid-19:	coronavirus disease 2019
dsDNA:	double-stranded DNA
ECG:	electrocardiogram, electrocardiogram
eCRF:	electronic case report form
EOS:	end-of-study
HGLT:	high level group term
HLGT:	high-level group term
HLT:	high-level term
IA:	interim analysis
ICF:	informed consent form
IMP:	investigational medicinal product
INR:	international normalized ratio
ITP:	immune thrombocytopenia
ITT:	Intent-to-treat, intent-to-treat
IV:	intravenous
LLOQ:	lower limit of quantification
LLT:	lower-level term
MCH:	mean corpuscular hemoglobin
MCV:	mean corpuscular volume
MedDRA:	medical dictionary for regulatory activities
NCI-CTCAE:	National cancer institute common terminology for adverse events, National cancer institute common terminology for adverse events
PCSA:	potentially clinically significant abnormality, potentially clinically significant abnormality
PD:	pharmacodynamics
PK:	pharmacokinetic
PT:	preferred term
RBC:	red blood cell

RNP:	Anti-Ribonucleoprotein antibody
SAP:	statistical analysis plan
SCL-70:	Anti-Scleroderma antibody
SD:	standard deviation
SGOT:	serum glutamic-oxaloacetic transaminase
SGPT:	serum glutamic-pyruvic transaminase
SLE:	systemic lupus erythematosus
Sm:	Anti-Smith antibody
SOC:	system organ class
SOC:	system organ class
SS-A:	Anti-Ro/SSA antibody
SS-B:	Anti-La/SSB antibody
TE:	treatment-emergent
TEAE:	treatment-emergent adverse event, treatment-emergent adverse event
ULOQ:	upper limit of quantification
WBC:	white blood cell
WHO:	World Health Organization
WHO-DD:	World Health Organization - drug dictionary, World Health Organization drug dictionary, World Health Organization-drug dictionary

## 5.2 APPENDIX 2 CHANGES TO PROTOCOL-PLANNED ANALYSES

Not applicable.

## 5.3 APPENDIX 3 DEMOGRAPHICS AND BASELINE CHARACTERISTICS, PRIOR OR CONCOMITANT MEDICATIONS

### *Demographics, baseline characteristics, medical surgical history*

The following demographics and baseline characteristics, medical and surgical history will be summarized using descriptive statistics in the exposed population.

#### Demographic and baseline characteristics

- age in years as quantitative variable and in categories (<65,  $\geq$ 65)
- gender (Male, Female)
- race (American Indian or Alaska Native, Asian, Black or African American, Native Hawaiian or Other Pacific Islander, White, Not Reported, Unknown)
- ethnicity (Hispanic or Latino, not Hispanic or Latino, Not Reported, Unknown)
- height (cm), weight (kg), body mass index (BMI) (kg/m $^2$ ).

Baseline safety and efficacy parameters (apart from those listed above) will be presented along with the safety and efficacy summaries.

The time (in years) from the date of ITP diagnosis to the date of first IMP administration will be summarized.

Medical and surgical history will be coded to a PT and associated primary SOC using the MedDRA currently in effect at Sanofi at the time of database lock.

The proportion of participants who had documented vaccines within 5 years and who have received vaccination during the study will be summarized. The vaccines include meningococcal vaccine, S. pneumoniae vaccine, and H. influenza vaccine. The type of the vaccine will be summarized.

### ***Prior or concomitant medications***

All medications will be coded using the World Health Organization-drug dictionary (WHO-DD) using the version currently in effect at Sanofi at the time of database lock.

- Prior medications are those the participant used prior to first IMP intake. Prior medications can be discontinued before first administration or can be ongoing during treatment period.
- Concomitant medications are any interventions received by the participant concomitantly to the IMP during the on-treatment period.
- Post-treatment medications are those the participant took in the period running from the end of the concomitant medications period up to the end of the study.
- A given medication can be classified as a prior medication and/or as a concomitant medication and/or as post-treatment medication. If it cannot be determined whether a given medication was taken prior or concomitantly or post, it will be considered as prior, concomitant, and post-treatment medication.

The prior, concomitant, and post-treatment non-ITP medications will be summarized for the ITT population, by anatomic and therapeutic level. The summaries will be sorted by decreasing frequency of anatomic category (ATC) based on incidence in intervention group. Therapeutic classes are sorted by decreasing frequency within each anatomic class. In case of equal frequency, alphabetical order will be used. Participants will be counted once in each ATC category (anatomic or therapeutic) linked to the medication.

Prior ITP, concomitant non-rescue ITP, and concomitant rescue ITP therapies/medications will be summarized separately by the ATC level 4 chemical class and medication name. All ITP therapies will be listed with rescue ITP therapies flagged.

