5.1 INCLUSION CRITERIA

Participants are eligible to be included in the study only if all the following criteria apply:

Age

I 01. Male and female participants ≥ 18 years of age at the time of signing the informed consent.

Type of participant and disease characteristics

I 02. Confirmed diagnosis of primary ITP; for participants who previously received sutimlimab in study TDR16218, a response to sutimlimab must have been obtained, as defined by platelet count $\geq 30 \times 10^9/L$ on 2 visits at least 7 days apart.

I 03. For participants who have not previously received sutimlimab: persistent/chronic ITP (ITP lasting for ≥ 6 months) and all the following conditions:

- a) Platelet count $\leq 30 \times 10^9/L$ on 2 occasions at least 5 days apart during the Screening Period;
- b) Lack of an adequate platelet count response (as defined by maintenance of sustained platelet count $\geq 30 \times 10^9/L$ in the absence of bleeding) to at least 2 ITP treatments, 1 of which was a thrombopoietin receptor agonist. Other ITP treatments include: IVIg, anti-D immunoglobulin, corticosteroids, splenectomy, rituximab, cyclophosphamide, azathioprine, danazol, cyclosporin A, mycophenolate mofetil, or fostamatinib.
- c) If receiving weekly thrombopoietin receptor agonist dosing, the last dose must have been administered ≥ 7 days before the first dose of BIVV020. If receiving daily thrombopoietin receptor agonist dosing, the last dose must have been administered ≥ 24 hours before the first dose of BIVV020.
- d) If applicable, concurrent administration of ITP medications (eg, corticosteroids, IVIg, azathioprine, danazol, cyclosporin A, mycophenolate mofetil, or thrombopoietin receptor agonists) is acceptable provided the patient has been on a stable dose for at least 1 month. See [Section 6.8](#) for additional details.
- e) If previously dosed with rituximab, the last dose of rituximab must have been administered at least 12 weeks before the first dose of BIVV020.
- f) If previously dosed with cyclophosphamide, the last dose of cyclophosphamide must have been administered at least 4 weeks before the first dose of BIVV020.

I 04. Documented vaccinations against encapsulated bacterial pathogens (*Neisseria meningitidis*, including serogroup B where available, *Haemophilus influenzae*, and *Streptococcus pneumoniae*) within 5 years of enrollment, or as specified in [Section 8.2.6](#).

Contraception

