### **4.3 PRIMARY ENDPOINT(S) ANALYSIS**

The primary endpoint is the proportions of participants who met the following criteria:

1. For naïve participants,
  - a platelet count  $\geq 50 \times 10^9/L$  OR
  - a  $\geq 20 \times 10^9/L$  increase from baseline if baseline platelet count  $< 15 \times 10^9/L$  at  $\geq 50\%$  of scheduled visits from Week 3 to Week 24.

For switchers, a platelet count  $\geq 30 \times 10^9/L$  at  $\geq 50\%$  of scheduled visits from Week 3 to Week 24.

2. No concomitant ITP therapy from Week 3 to Week 24.

Concomitant medications are defined in [Section 5.3](#). The ITP therapies will be identified by the Sanofi coding group, reviewed by medical, and defined in the programming specifications. The ITP therapies include corticosteroids, thrombopoietin receptor agonists, intravenous immunoglobulin, anti-D immunoglobulin, rituximab, fostamatinib, immunosuppressants (azathioprine, cyclosporin A, mycophenolate mofetil), cyclophosphamide, dapsone, danazol.

The response rate will be summarized for naïve participants, switchers, and total for the ITT along with the 95% exact Clopper-Pearson Confidence Interval (CI).

Platelet counts will be summarized by visit. These plots will also be provided:

- Individual platelet count profile: line plot of platelet count by visit for each participant

- Spaghetti plot platelet count by participant
- Median platelet count/change from baseline with by visit

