##### **The proportion of participants who met the following criteria at Week 24/Week 56:**

1. A platelet count  $\geq 50 \times 10^9/L$  and a greater than 2-fold increase from baseline, measured on 2 occasions at least 7 days apart.
2. No bleeding while the platelet counts are maintained above the threshold. Bleeding is defined as bleeding with a score  $\geq 2$  on the World Health Organization (WHO) bleeding scale ([Section 5.5](#)) collected in the eCRF.
3. No concomitant ITP therapy while the platelet counts are maintained above the threshold.

The response rate will be summarized at Week 24 and Week 56 separately for the ITT along with the 95% exact Clopper-Pearson CI.

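### The SAP's default for medications of undeterminable timing feeds the responder criteria, and the SAP does not say whether such a record counts within Week 3 to Week 24

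*SAP*

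**What the plan says.** **Default rule (SAP Section 5.3, Prior or concomitant medications).** The rule is: "If it cannot be determined whether a given medication was taken prior or concomitantly or post, it will be considered as prior, concomitant" and also as post-treatment. In the same list, "Concomitant medications are any interventions received by the participant concomitantly to the IMP during the on-treatment period". SAP Section 4.1 sets that period as first IMP administration to last administration plus 7 days.

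**Primary endpoint (SAP Section 4.3).** Criterion 2 is "No concomitant ITP therapy from Week 3 to Week 24". The text below it begins "Concomitant medications are defined in" and points to Section 5.3. It then lists the drug classes that count as ITP therapy and says that coding and medical review will identify them.

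**Secondary response at Week 24/Week 56 (SAP Section 4.4).** Criterion 3 is "No concomitant ITP therapy while the platelet counts are maintained above the threshold".

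**Protocol endpoint (Protocol Section 3, Table 2; repeated in SAP Section 1.2, Table 1).** The primary condition is the absence of rescue ITP therapy from Week 3 to Week 24. Protocol Section 6.8.1 says what rescue is, and includes raising the dose of a concomitant ITP medication because of low platelet counts.

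**History (Protocol Section 5.1, I 03 b).** Naïve participants must have lacked an adequate response "to at least 2 ITP treatments, 1 of which was a thrombopoietin receptor agonist".

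**The concern.** Counting an unplaceable medication in every period is a usual convention for medication tables, where it can only over-list a drug. Here the same definition decides who is a responder. A record with no usable timing can become concomitant ITP therapy by default and so count against the participant. The error runs one way: it can lower the response rate but cannot raise it.

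Naïve participants enter with a treatment history, so old ITP courses will be in the database. If a record does not show whether a course had ended, the primary classification depends on how completely history was recorded and on a choice the SAP leaves to the programmer. With about 12 participants, one such choice is visible in the headline proportion.

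**Working it through.** The plan gives no figure to reproduce: it tests no hypothesis, and the sample size is not derived statistically (Protocol Section 9.1; SAP Section 2). The check is a trace of the rules, followed by the size of one reclassified participant.

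**Step 1. Does the default reach the endpoint?** Yes. SAP 4.3 criterion 2 uses the term concomitant and refers to SAP 5.3, which contains the default. Neither section limits the default to summary tables or exempts ITP drugs. The medical review in SAP 4.3 settles which drugs are ITP therapies, not when they were taken. The SAP has no imputation rule for missing or partial medication dates. SAP 4.4 criterion 3 uses the same term without another definition.

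**Step 2. Which records trigger it?** Only those whose period of use cannot be determined. A record showing that the course ended before Day 1, even with a partial stop date, is prior only. The label prior is not enough without evidence of an end, because SAP 5.3 allows a prior medication to be ongoing during treatment and Protocol 5.1 I 03 d permits stable background ITP drugs.

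**Step 3. Is a default-concomitant record inside Week 3 to Week 24?** The SAP does not say. Concomitant covers the whole on-treatment period, which is wider than the window. Criterion 3 in SAP 4.4 leaves the same question for its own period.

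**Step 4. Consequence if it is counted inside.** Take a naïve participant with platelets of 80 × 10⁹/L at every assessed visit, no rescue therapy, and one danazol record that does not show whether the course had ended. Danazol is on the SAP 4.3 list. Criterion 1 is met and criterion 2 fails, so the participant is a non-responder. Under the protocol endpoint the same participant is a responder.

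**Step 5. Size of one case.** Inputs: about 12 participants, of whom up to 6 are switchers (Protocol Section 4.1). If 12 enroll, at least 12 − 6 = 6 are naïve. Four patients were still on sutimlimab in TDR16218 on 29 September 2020 (Protocol Section 2.3). If those four are the only switchers, 12 − 4 = 8 are naïve.

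- Total: 1/12 = 8.3 points
- Naïve, n=6: 1/6 = 16.7 points
- Naïve, n=8: 1/8 = 12.5 points

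Illustration with the planned exact Clopper-Pearson 95% intervals:

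| Group | Without the reclassification | With one responder reclassified |
|---|---|---|
| n=12 | 6/12 = 50.0% (21.1 to 78.9) | 5/12 = 41.7% (15.2 to 72.3) |
| n=6 | 3/6 = 50.0% (11.8 to 88.2) | 2/6 = 33.3% (4.3 to 77.7) |

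**Step 6. How often?** The documents give no rate. As an assumption only, let q be the chance that a true responder has an undeterminable ITP record, and suppose there are 6 true responders. The chance of losing at least one is 1 − (1 − q)⁶: 11.4% at q = 2%, 26.5% at 5%, 46.9% at 10% and 73.8% at 20%. All four figures also assume that Step 3 is resolved by counting the record in the window.

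**The case against.** The strongest case on the other side has five parts.

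- **The trigger is narrow.** A reader might infer that any undated historical ITP drug makes a participant a non-responder. The documents do not support that. A missing date is not an undeterminable period, and a course known to be past is prior only.
- **The loss is not stated.** A reader might infer that the SAP itself scores such participants as failures. It does not, because nothing places a default-concomitant record in Week 3 to Week 24. This stands, but a primary classification left open is still a gap that the SAP should close.
- **Other text limits exposure.** Protocol Section 6.8 requires start and end dates for medication taken at enrollment or during the study. Protocol 5.1 I 03 c, e and f require last-dose timing for current thrombopoietin receptor agonists and for any past rituximab or cyclophosphamide. This narrows the problem but does not remove it: that sentence of Section 6.8 does not cover courses that ended earlier, and past danazol, azathioprine, cyclosporin A or mycophenolate has no such eligibility check.
- **The larger problem is elsewhere.** SAP 4.3 fails any concomitant ITP therapy where the protocol fails only rescue, and correcting that would remove most of this issue. This is right for the primary endpoint, and the fix below includes it. It does not settle SAP 4.4 criterion 3, which is not limited to rescue.
- **The consequence is modest.** The trial is descriptive, and SAP 5.3 lists all ITP therapies with rescue flagged, so a careful reader could spot a case. That lowers the stakes, but the reported proportion and interval would still be wrong.

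**Conclusion.** The concern holds in a limited form. SAP 5.3's default reaches the responder criteria in SAP 4.3 and 4.4 with no exemption, and the SAP does not say whether a record that is concomitant only by default counts in the assessment period. If it does, an otherwise qualifying participant is scored as a non-responder on a ground that the protocol's primary endpoint does not contain. SAP Appendix 2 records no change from the protocol.

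Each case costs 8.3 points in a total of 12 and up to 16.7 points among naïve participants (n=6; 12.5 if n=8). These sizes assume that 12 enroll, that the participant meets the platelet criterion, and that the record is counted in the window.

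Two further inferences are tempting and unsupported. The two failed treatments required by I 03 b do not guarantee two ITP drug records, because that criterion also accepts splenectomy, which is not on the SAP 4.3 list. And an assumed chance of having an undeterminable record is not the chance of losing a responder, since the participant must also otherwise qualify.

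**What to change.** Amend the SAP before the responder derivations are programmed:

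1. In Section 5.3, limit the default to the descriptive medication tables.
2. In Section 4.3, align criterion 2 with the protocol: only rescue ITP therapy shown to be given in Week 3 to Week 24 counts as failure, including a dose increase of background ITP medication as described in Protocol Section 6.8.1. An ongoing status alone should not count, because the protocol permits stable background ITP medication.
3. In Section 4.4 criterion 3, count an ITP therapy only when its record shows use in the relevant period.
4. Treat records identified as prior ITP treatment with missing or partial dates as prior.
5. Report a sensitivity analysis in which undeterminable records count as failures.

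The cost is a few SAP sentences, one programming condition and one extra table. The downside is small: an undated drug truly given on treatment could be missed in the main analysis, and the sensitivity analysis would show by how much that could matter.

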## 5.4 APPENDIX 4 DATA HANDLING CONVENTIONS

### Study Day

Study Day is defined as days relative to the date of first IMP administration (ie, D1 as in the protocol). The Study Day of an event is calculated as

- (date of event – date of first IMP administration + 1), if the event is on or after the first IMP administration;
- (date of event – date of first IMP administration), if the event is prior to the first IMP administration.

The date of the first IMP administration is Study Day 1.

### Analysis windows for time points

The following analysis windows will decide how the scheduled and/or unscheduled visits will be used in the by-visit analyses of efficacy, safety, PK and ADA variables.

A measurement (scheduled or unscheduled) will be used if it is available and measurement date is within the analysis window.

After applying these time windows, if multiple assessments are associated to the same time point, the closest from the targeted study day will be used. If the difference is a tie, the value after the targeted study day will be used. If multiple valid values exist within a same day, then the first value of the day will be selected.

If there is no measurement for a given parameter in an analysis window, data will be considered missing for the corresponding visit.

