8.1 EFFICACY ASSESSMENTS

Planned time points for all efficacy assessments are provided in the SoA ([Section 1.3](#)). The primary efficacy endpoint is determined by platelet counts, which will be assessed by a central lab.

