10.2 APPENDIX 2: CLINICAL LABORATORY TESTS

- The tests detailed in [Table 6](#) will be performed by the central laboratory unless otherwise specified.
- Local laboratory results are only required in the event that the central laboratory results are not available in time for either study intervention administration and/or response evaluation. If a local sample is required, it is important that the sample for central analysis is obtained at the same time. Additionally, if the local laboratory results are used to make either a study intervention decision or response evaluation, the results must be recorded.
- Additional tests may be performed at any time during the study as deemed necessary by the Investigator or required by local regulations.
- Pregnancy testing (serum and urine) will be performed locally.
- SARS-CoV-2 testing, if applicable, will be performed through the central lab.

Table 6 - Protocol-required laboratory tests

Laboratory tests	Parameters
Hematology	
Platelet count
 
Red blood cell (RBC) count
 
Hemoglobin
 
Hematocrit
 
RBC indices (at minimum):
 
Mean corpuscular volume (MCV)
 
Mean corpuscular hemoglobin (MCH)
 
White blood cell (WBC) count with differential:
 
WBC
 
Neutrophils
 
Lymphocytes
 
Monocytes
 
Eosinophils
 
Basophils

Clinical chemistry	
Blood urea nitrogen (BUN)
 
Creatinine
 
Glucose (non-fasting)
 
Potassium
 
Sodium
 
Calcium
 
Aspartate aminotransferase (AST)/Serum glutamic-oxaloacetic transaminase (SGOT)
 
Alanine aminotransferase (ALT)/Serum glutamic-pyruvic transaminase (SGPT)
 
Alkaline phosphatase^a
 
Total and direct bilirubin
 
Total protein

Laboratory tests	Parameters
Coagulation	Prothrombin time (PT)/international normalized ratio (INR) Activated partial thromboplastin time (aPTT)
SLE panel	Antinuclear antibody (ANA) Double-stranded DNA (dsDNA) Anti-La/SSB antibody (SS-B) Anti-Ribonucleoprotein antibody (RNP) Anti-Smith antibody (Sm) Anti-Ro/SSA antibody (SS-A) Anti-Scleroderma antibody (SCL-70) Anti-Chromatin antibody Anti-Jo-1 antibody Anti-Centromere B antibody Circulating immune complexes (CIC)
Other	Serum creatine kinase (CK) (at Screening only) Follicle-stimulating hormone (FSH) (at Screening only, if indicated; see Section 10.4.1) CH50

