10.8 APPENDIX 8: COUNTRY-SPECIFIC REQUIREMENTS

Not applicable.

10.9 APPENDIX 9: CONTINGENCY MEASURES FOR A REGIONAL OR NATIONAL EMERGENCY THAT IS DECLARED BY A GOVERNMENTAL AGENCY

The following contingencies may be implemented for the duration of the emergency (after Sponsor agreement is obtained).

Study intervention

If a participant has to stop BIVV020 due to a regional or national emergency (eg, COVID-19), re-initiation of the study intervention can only occur once the Investigator has determined, according to his/her best judgement, that 1) BIVV020 did not contribute to the occurrence of the concerned adverse event and 2) the selection criteria for the study are still met (refer to [Section 5](#)). Re-initiation of the study intervention will be done under close and appropriate clinical/and or laboratory monitoring and in consultation with the Sponsor.

Study assessments and procedures

During the emergency, if the site will be unable to adequately follow protocol mandated procedures, alternative treatment outside the clinical trial should be proposed, and screening/enrollment/administration of study intervention may be temporarily delayed.

Attempts should be made to perform all assessments in accordance with the approved protocol to the extent possible. In case this is not possible due to a temporary disruption caused by an emergency, focus should be given to assessments necessary to ensure the safety of participants and those important to preserving the main scientific value of the study.

Procedures to be considered in the event of a regional or national emergency declared by a governmental agency:

- If onsite visits are not possible, remote visits (eg, with home nurses, home health vendor, etc) may be planned for the collection of possible safety and/or efficacy data.
- If onsite visits are not possible, visit windows may be extended for assessment of safety and/or efficacy data that cannot be obtained remotely.
- Use of local clinic or laboratory locations may be allowed when central labs cannot be performed due to a government declared national emergency.

Statistical analyses

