## **Quantitative analyses**

For all laboratory variables, vital signs and ECG variables above, descriptive statistics for results and changes from baseline will be provided for each planned visit, the last value during the on-treatment period. These analyses will be performed using central measurements only (when available) for laboratory variables.

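### SAP 5.4 lets an unscheduled platelet count displace the scheduled one, on the natural reading also in the primary endpoint, and leaves the laboratory source for efficacy unstated; the likely effect is small.

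*SAP*

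**What the plan says.** **Protocol.** Section 8.1 fixes the laboratory: "The primary efficacy endpoint is determined by platelet counts, which will be assessed by a central lab". Table 2 defines the primary endpoint by the share of scheduled visits from Week 3 to Week 24 at which the count meets its threshold. Two provisions allow for local results:

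- Section 10.2: "Local laboratory results are only required in the event that the central laboratory results are not available in time" for dosing or response evaluation. In that case "it is important that the sample for central analysis is obtained at the same time", and "if the local laboratory results are used to make either a study intervention decision or response evaluation, the results must be recorded".
- Section 10.9 (emergencies): "Use of local clinic or laboratory locations may be allowed when central labs cannot be performed due to a government declared national emergency".

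Section 8 also permits unscheduled samples for safety or technical reasons.

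**SAP.** Section 4.3 repeats the scheduled-visit definition. It names no laboratory and does not mention unscheduled counts. Section 5.4 sets the windows for by-visit analyses, efficacy included. It admits any count: "A measurement (scheduled or unscheduled) will be used if it is available and measurement date is within the analysis window". It then selects: "if multiple assessments are associated to the same time point, the closest from the targeted study day will be used". A tie goes to the value after the target day, and several values on one day are resolved by taking the first. The scheduled count has no priority.

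Elsewhere the SAP is explicit. For safety summaries by visit (4.6.3.1) it states: "These analyses will be performed using central measurements only (when available) for laboratory variables". For potentially clinically significant abnormalities it admits local and central values alike. For time to response (4.4) it includes unscheduled counts. SAP 5.2 declares no change to the protocol's planned analyses.

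**The concern.** Each visit is scored against a hard cut-off: 50 for naïve participants, 30 for switchers, or baseline plus 20 for naïve participants with a baseline below 15 (all ×10⁹/L). The trial is open-label, and the investigator reviews the laboratory results. A repeat is more likely after a surprising count, and a repeat of an unusually low count tends to be higher simply through regression to the mean. If the repeat replaces the scheduled value, the decision to draw blood again becomes part of how the primary endpoint is scored.

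The laboratory gap is separate. Protocol 10.2 can produce a local and a central count from the same moment, and SAP 5.4 does not say which one is scored. Two programmers could follow this SAP and score the same visit differently.

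**Working it through.** The plan gives no figure to reproduce: no hypothesis is tested and the sample size is not derived statistically. The check applies the SAP 5.4 rule literally.

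**Inputs from the documents**

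- Windows (SAP Table 6): ±1 day for Days 22 to 43, ±2 for Weeks 8 to 12, ±3 for Weeks 16 and 20, ±4 for Week 24.
- Visits from Week 3 to Week 24: 10 if every on-site visit has a count (SAP 1.1). The platelet row of the protocol's schedule, as far as it can be read, suggests 8 (Days 29 and 43, Weeks 8, 10, 12, 16, 20, 24).
- About 12 participants, up to 6 of them switchers.

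Table 6 gives Week 10 a target of Day 80 (window 78 to 82), but the protocol's Week 10 visit falls on Day 7 × 10 + 1 = 71 (69 to 73). As printed, only an unscheduled or badly off-schedule count could fill Week 10. The calculation below uses Day 71.

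**Step 1: which count wins.** Let *s* and *u* be the distances in days of the scheduled and unscheduled counts from the target. The unscheduled count wins if |u| < |s|, or if |u| = |s| and u > s. Over all pairs on different days of a window it wins in 3 of 6 (±1), 10 of 20 (±2), 21 of 42 (±3) and 36 of 72 (±4), always half. A scheduled count on the target day can lose only to an earlier count that same day.

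**Step 2: how often a later repeat displaces a low count.** Suppose the scheduled count was *k* days early. A repeat *d* days later wins exactly when d ≤ 2k. If the scheduled count was on or after the target, a later repeat never wins. Assume the scheduled day is uniform over the window ±w and *d* is uniform on 1 to G. Then

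P(w) = [1/(2w+1)] × Σ min(2k, G)/G, summed over k = 1 to w.

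| Window | G = 7 | G = 3 |
|---|---|---|
| ±1 | (1/3)(2/7) = 0.095 | 0.222 |
| ±2 | (1/5)(6/7) = 0.171 | 0.333 |
| ±3 | (1/7)(12/7) = 0.245 | 0.381 |
| ±4 | (1/9)(19/7) = 0.302 | 0.407 |

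Over the 8 visits (two at ±1, three at ±2, two at ±3, one at ±4) the mean for G = 7 is (2×0.095 + 3×0.171 + 2×0.245 + 0.302)/8 = 0.187. For G = 3 it is 0.327. If 25% or 50% of low counts are repeated, the share displaced is 4.7% or 9.4% (G = 7) and 8.2% or 16.3% (G = 3).

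**Step 3: effect on the responder rate.** Simulation with these assumptions, none from the documents: threshold 50, response at 4 or more of 8 visits, participant medians log-uniform from 25 to 120, visit-to-visit log-SD 0.3 or 0.5, repeat independent of the count it replaces.

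| Low counts repeated | Delay (days) | Rise, log-SD 0.3 | Rise, log-SD 0.5 |
|---|---|---|---|
| 25% | 1–7 | 0.55 points | 0.92 points |
| 50% | 1–7 | 1.09 | 1.82 |
| 25% | 1–3 | 0.95 | 1.60 |
| 50% | 1–3 | 1.87 | 3.15 |

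With 10 visits (5 needed) the rises are 0.5 to 3.0 points. Runs of this kind lie between 0.4 and 3.2 points.

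**Step 4: scale.** One participant of 12 is 1/12 = 8.3 points, so a rise of 3.2 points is 0.032 × 12 = 0.38 of a participant. The exact 95% interval is 21.1% to 78.9% for 6/12 and 27.7% to 84.8% for 7/12. In a subgroup of 6, one participant is 16.7 points. If visits are independent with success probability 0.3 to 0.6 (assumed), 12% to 28% of participants are exactly one visit short with 8 visits, and 11% to 25% with 10. For them a single displaced count can decide the result.

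**The case against.** **Nearest-to-target selection is prespecified and does not look at the value.** This is true of the selection. The decision to draw a repeat may still depend on the value, and the rule gives the scheduled visit, on which the endpoint is defined, no priority.

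**The rule may not reach the primary endpoint.** SAP 5.4 speaks of by-visit analyses. Where the SAP wants unscheduled counts in an efficacy endpoint (time to response) it says so, and SAP 4.3 does not. This stands as a caveat. Still, the endpoint is built from visits, the windows expressly cover efficacy, and no other rule assigns counts to visits.

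**A reader might infer that the SAP replaces central counts with local ones.** The documents do not support that. SAP 5.4 contrasts scheduled with unscheduled and never mentions local counts. Protocol 8.1 stays in force because SAP 5.2 declares no change, and Protocol 10.2 asks for a central sample alongside any required local one. What remains is the SAP's silence on laboratory source for efficacy.

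**A reader might also infer a sizeable upward bias.** Replacing 25% to 50% of all low counts with fresh values would raise the rate by about 3 to 9 points under the same count model. The window rule does not work that way. With repeats 1 to 7 days later, even repeating every low count displaces only 18.7% of them. With repeats within 3 days, about three quarters of low counts would have to be repeated to displace 25% (0.25/0.327 = 0.76).

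**The direction is not fixed.** A draw prompted by bleeding may be low and displace a higher scheduled count. ITP therapy between Week 3 and Week 24 makes the participant a non-responder under SAP 4.3 whatever the counts. Treating repeats as independent also overstates the rise. These points stand.

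**Conclusion.** The point holds as a gap between the endpoint definition and the data-handling rule. SAP 5.4 allows an unscheduled count to displace the scheduled one. On the natural reading this reaches the primary responder endpoint, and the laboratory source for efficacy is not stated. The likely effect on the response rate is about 0.4 to 3 points, well under one participant of 12 and small beside the interval width. That range rests on assumed repeat rates of 25% to 50% of low counts, delays of 1 to 7 or 1 to 3 days, and the count model above. It makes no allowance for rescue therapy or for repeats that come out low. No sample-size or power figure is affected. This is a minor clarification, worth making because individual participants can sit one visit from the cut-off.

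**What to change.** Add to SAP 4.3, with a cross-reference in 5.4, a rule such as:

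> For each visit scored in the platelet responder endpoint, use the central-laboratory count from the scheduled visit. If that count is missing or not evaluable, use an unscheduled or local count within the visit window, taking the earliest such count, and flag the substitution in the listing.

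Leave the time-to-response rule in SAP 4.4 unchanged, since it deliberately uses unscheduled counts. Reconcile the Week 10 target day at the same time, because the fallback needs a window that matches the visit.

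The cost is one or two sentences and a selection flag in programming, with no new data. The downside is that a few visits will use a count slightly further from the target day.
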